6.2.12 Follow-Up Visits 1 and 2 (Week 12 and Week 26)

During Follow-Up Visits 1 and 2 (Duration: ~30 minutes) participants will:

1. Perform a CO breath assessment or provide a urine sample for a cotinine assessment, answer combustible marijuana items, and complete a concomitant medication review.
2. Provide daily smoking rate (timeline follow back [TLFB]).
3. Have weight measured.
4. Complete paper and pencil questionnaires:
 - Adverse Events Form (Open-Ended AEs)
 - Physical Activity (PAR)
5. If a participant reports not smoking (not even a puff of a cigarette) for at least the 7 days prior to the Follow-Up Visit without the aid of NRT, the participant will be asked to provide a 5ml saliva sample used to assess cotinine levels and verify abstinence from smoking.
6. Confirm the 24-hour dietary recall (Week 12 [#4] and Week 26 [#5]) schedule.

6.2.13 fMRI Scan Visits 1 & 2 (~Week -2 and ~Week 7-8)

Participants who are both eligible and elect to participate in the neuroimaging sub-study will complete two neuroimaging sessions: Scan 1 will occur prior to the Baseline Visit (~week -2) and Scan 2 will occur during the final week of nicotine patch therapy (~week 7-8). Prior to each scan, participants will be instructed to fast overnight (beginning at ~10pm) until after the

CONFIDENTIAL

This material is the property of the University of Pennsylvania. Do not disclose or use except as authorized in writing by the study sponsor

completion of their fMRI scanning visit the following day. The fast period does not include a Boost® Nutritional Drink (Vanilla) that will be provided during the scanning visit to standardize prior food intake and remove deprivation to increase sensitivity to changes in food reward. Since participants are asked to fast overnight, all scanning sessions will be scheduled to occur in the morning. However, a scan may be completed in the afternoon at the discretion of the Principal Investigator due to extenuating circumstances. Additionally, participants will be instructed not to consume caffeine for 4 hours prior to the beginning of the visit in order to standardize satiety. Including the 1-hour fMRI scan, scanning visits are expected to last ~3 hours in duration. If a scanner hardware/software malfunction occurs and data is unable to be collected, an fMRI scan(s) may be rescheduled at the discretion of the Principal Investigator.

At both scanning visits participants will:

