1. Complete a urine drug screen (at least 30ml [two tablespoons] of urine). The urine drug screen will assess the use of any study-prohibited medications/recreational drugs (See Key Exclusionary Criteria; Alcohol/Drugs). Participants who test positive for any study-prohibited medications/recreational drugs will not be permitted to complete the neuroimaging sub-study and may be deemed ineligible for the main study at the discretion of the Principal Investigator.
2. Self-administer a CLIA-waived urine pregnancy test (female participants only). Participants who believe that they may be pregnant are instructed to discontinue participation in both the neuroimaging sub-study and parent study at this time.
3. Perform a BrAC assessment to control for alcohol consumption.
 - Participants with a BrAC greater than 0.010 will be ineligible to complete the neuroimaging sub-study (may remain in the parent study) unless the Principal Investigator permits the participant to reschedule the neuroimaging scan to another day.
4. Perform a CO breath assessment, answer combustible marijuana items, and complete a concomitant medication review.
5. Self-report smoking behavior over the past 24 hours to control for prior tobacco exposure and provide their daily smoking rate (timeline follow back [TLFB]).
6. Have weight measured.
 - Participants weighing over 300 lbs will be ineligible to complete the neuroimaging sub-study. However, participants may remain enrolled in the main study.
7. **SCAN 2 ONLY:** Provide TN progress and adherence information.
8. **SCAN 2 ONLY:** Complete paper and pencil questionnaires:
 - Side Effect Checklist (SEC)
 - Adverse Events Form (Open-Ended AEs)
9. Complete a magnet safety form.
 - Participants who do not meet the fMRI eligibility criteria will be deemed ineligible for the neuroimaging sub-study. Participants may still participate in the parent study per protocol.
10. Complete a set of abbreviated practice tasks similar to those that will be administered during the fMRI scan, as well as an individualized calibration task to determine the amount of food (i.e. "Food Value Number") that is equivalent to \$0.25 in order to calculate the standard portion size of a participant's preferred snack food (i.e. chips or M&Ms®) that may be earned on a given trial within the in-scanner Food

CONFIDENTIAL

This material is the property of the University of Pennsylvania. Do not disclose or use except as authorized in writing by the study sponsor

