8.1 Definitions

Unanticipated Problems Involving Risk to Subjects or Others:

Any incident, experience, or outcome that meets all of the following criteria:

CONFIDENTIAL

This material is the property of the University of Pennsylvania. Do not disclose or use except as authorized in writing by the study sponsor

- Unexpected in nature, severity, or frequency (i.e. not described in study-related documents such as the IRB-approved protocol or consent form, the investigators brochure, etc.)
- Related or possibly related to participation in the research (i.e. possibly related means there is a reasonable possibility that the incident, experience, or outcome may have been caused by the procedures involved in the research)
- Suggests that the research places subjects or others at greater risk of harm (including physical, psychological, economic, or social harm).

Adverse Event:

An **adverse event** (AE) is any symptom, sign, illness or experience that develops or worsens in severity during the course of the study (regardless if TN related). Intercurrent illnesses or injuries should be regarded as adverse events. Abnormal results of diagnostic procedures are considered to be adverse events if the abnormality:

- results in study withdrawal
- is associated with a serious adverse event
- is associated with clinical signs or symptoms
- leads to additional treatment or to further diagnostic tests
- is considered by the investigator to be of clinical significance

Serious Adverse Event:

Adverse events are classified as serious or non-serious. A **serious adverse event** (SAE) is any AE that is:

- fatal
- life-threatening
- requires or prolongs hospital stay
- results in persistent or significant disability or incapacity
- a congenital anomaly or birth defect
- an important medical event

Important medical events are those that may not be immediately life threatening, but are clearly of major clinical significance. They may jeopardize the subject, and may require intervention to prevent one of the other serious outcomes noted above. For example, drug overdose or abuse, a seizure that did not result in in-patient hospitalization, or intensive treatment of bronchospasm in an emergency department would typically be considered serious.

All adverse events that do not meet any of the criteria for serious should be regarded as **non-serious adverse events**.

Adverse Event Reporting Period:

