The study period during which AEs/SAEs will be reported is from the initiation of any study procedures until the end of the study. Any event(s) that the subject, or the subject's personal physician, believes might reasonably be related to participation in the study after the final time point will be assessed and reported as appropriate.

Preexisting Condition:

A preexisting condition is one that is present at the start of the study. A preexisting condition should be recorded as an adverse event if the frequency, intensity, or the character of the condition worsens during the study period.

Post-study Adverse Event:

CONFIDENTIAL

This material is the property of the University of Pennsylvania. Do not disclose or use except as authorized in writing by the study sponsor

All unresolved adverse events should be followed by the investigator until the events are resolved, the subject is lost to follow-up, or the adverse event is otherwise explained. At the last scheduled visit, the investigator should instruct each subject to report any subsequent event(s) that the subject, or the subject's personal physician, believes might reasonably be related to participation in this study.

Hospitalization, Prolonged Hospitalization or Surgery:

Any AE that results in hospitalization or prolonged hospitalization should be documented and reported as a SAE unless specifically instructed otherwise in this protocol. Any condition responsible for surgery should be documented as an AE if the condition meets the criteria for an AE.

Neither the condition, hospitalization, prolonged hospitalization, nor surgery are reported as an adverse event in the following circumstances:

- Hospitalization or prolonged hospitalization for diagnostic or elective surgical procedures for a preexisting condition. Surgery should **not** be reported as an outcome of an adverse event if the purpose of the surgery was elective or diagnostic and the outcome was uneventful.
- Hospitalization or prolonged hospitalization required to allow efficacy measurement for the study.
- Hospitalization or prolonged hospitalization for therapy of the target disease of the study, unless it is a worsening or increase in frequency of hospital admissions as judged by the clinical investigator.

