8.2 Collection and Recording of Adverse Events

8.2.1 AE Collection Methods

All AEs and SAEs occurring during the study period will be captured through the methods described below:

1. **SEC:** Participants will complete an SEC at all in-person visits during the treatment period (including Pre-Quit as a baseline measure) after the Baseline Visit. The SEC will assess the severity of side effects that may be TN related and experienced by participants in the study (See section 7.1: Potential Study Risks; Transdermal Nicotine). These reports will be formally documented as **anticipated (expected)** AEs whether or not the event(s) is ultimately deemed related or not related to the use of TN in this study. The reporting period for each assessment will inquire about any side effects experienced since the last in-person visit. Items will be rated by participants utilizing the following severity scale: 0 (None=No Concerns), 1 (Mild=Side effect does not interfere with usual daily activities), 2 (Moderate= Side effect does interfere with some activities), and 3 (Severe=No normal activities are possible). Any side effect rated **severe or moderate** will require additional follow up per the internal reporting procedures outlined below in section 8.2.2. **Mild skin redness, skin rash, skin swelling, irregular heartbeat, or heart palpitations** also require additional follow up per the internal reporting procedures outlined below in section 8.2.2. Other side effects reported as mild, but not identified above, do **not** require additional follow up from the research staff or communication with the Project Manager, Study Physician, and Principal Investigator. However, these mild reports are maintained within the data management system and are available via aggregate report.
2. **Open-Ended AE Form:** Participants will be asked an open-ended question about any symptom or medical event that may be related to their study participation **not** included on the SEC form at all in-person visits after the Baseline Visit. These events will be

CONFIDENTIAL

This material is the property of the University of Pennsylvania. Do not disclose or use except as authorized in writing by the study sponsor

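### Scheduled adverse-event questions are narrower than the protocol's own AE definition and reporting period, so the statement that all AEs and SAEs will be captured is not supported

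*Combined protocol and SAP*

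**What the plan says.** Section 8.1 (Definitions) describes an adverse event as "any symptom, sign, illness or experience that develops or worsens in severity during the course of the study (regardless if TN related"), and adds: "Intercurrent illnesses or injuries should be regarded as adverse events". The reporting period runs "from the initiation of any study procedures until the end of the study". An AE that leads to hospitalization is an SAE, with listed exceptions that do not turn on causality.

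Section 8.2.1 (AE Collection Methods) states: "All AEs and SAEs occurring during the study period will be captured through the methods described below". It then lists three methods:

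- **SEC.** Given at in-person visits in the treatment period, starting at Pre-Quit. Its items are recorded whether or not they are later judged related to the patch.
- **Open-Ended AE Form.** Given at in-person visits after Baseline. It asks about "any symptom or medical event that may be related to their study participation not included on the SEC form". Section 6.5.2 repeats this scope.
- **Spontaneous assessment.** Enrolled participants are told to inform staff of notable symptoms or medical events at any time.

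Both forms look back to the last in-person visit. Section 8.2.2 gives the judgement of relatedness to the Principal Investigator and/or Study Physician. At weeks 12 and 26, section 6.2.12 lists the open-ended form and the physical activity recall as the questionnaires, with no SEC. Section 6.5.2, however, has the SEC completed at every in-person visit after Baseline. In section 6.2.13 both AE forms fall under "SCAN 2 ONLY: Complete paper and pencil questionnaires".

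**The concern.** The definition is broad and independent of cause, whereas the scheduled open question carries a relatedness condition. As described, the person applying that condition at the visit is in practice the participant, before the investigator or physician assigned the judgement in 8.2.2 sees anything. An intercurrent illness or injury that the participant thinks has nothing to do with the study counts as an AE under 8.1 but is not asked about.

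Two gaps in timing add to this. The open form excludes SEC items even at visits where, on the main reading, no SEC is given. The first look-back also begins later than the reporting period.

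What is at stake is the completeness of the safety record. The FDA and IRB reporting rules in 8.3 work from investigator judgements of relatedness and expectedness. Those judgements can be made only on events that were elicited or volunteered.

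**Working it through.** The plan gives no figure for AE capture, so there is none to reproduce. The check sets the definition, the collection methods and the visit lists side by side.

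**Inputs**
- AE definition and reporting period: 8.1.
- Scope and timing of the two forms: 6.5.2 and 8.2.1.
- Visit contents: Intake (6.2.2), Baseline (6.2.3), Pre-Quit (6.2.4), End of Treatment (6.2.10), follow-ups (6.2.12), scans (6.2.13).
- Patch treatment from week 0 to week 8: 5.2.
- Table 2 was not used, because its columns do not align reliably in the text available for review.

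**Step 1. Which scheduled form asks about which event?**

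| Event | Intake to Baseline | After Baseline to week 8 | After week 8 (asked at weeks 12 and 26) |
|---|---|---|---|
| SEC-type symptom | Neither form | SEC, related or not | Neither under 8.2.1 and 6.2.12; SEC under 6.5.2 |
| Not on SEC, participant thinks it may be related | Neither form | Open form | Open form |
| Not on SEC, participant thinks it unrelated | Neither form | No scheduled question | No scheduled question |

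All three rows are AEs under 8.1. The bottom row has no scheduled question at any point.

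**Step 2. After treatment.** The last SEC listed for the parent study is at week 8 and the last visit is at week 26: 26 − 8 = 18 weeks. The two follow-up visits have look-backs of 12 − 8 = 4 weeks and 26 − 12 = 14 weeks. If the SEC is not given, both rest on an open form that excludes SEC items. Section 8.2.1 itself identifies skin redness, rash, swelling, irregular heartbeat and palpitations as SEC items, so these would be asked about by neither form.

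**Step 3. Before Baseline.** Intake and Baseline list no AE form. Both forms first appear at Pre-Quit and look back to the last in-person visit, which is Baseline. Intake is at about week −3 and Baseline at about week −2: −2 − (−3) = 1 week. Section 6.2.13 places Scan 1, with its overnight fast, before Baseline and gives the AE forms at Scan 2 only. Events between Scan 1 and Baseline therefore also fall outside both look-backs. Section 4.3 expects about 75 imaging enrollees to yield about 50 completers.

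**Step 4. Does the third method fill the remaining cells?** Spontaneous assessment has no relatedness limit and applies throughout participation. It depends on the participant starting the contact and on the event being considered notable. The 8.1 definition has no such threshold, so the three methods together still fall short of it.

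**The case against.** The strongest reply is that the capture statement rests on all three methods together, and the third has no relatedness limit. A reader might infer that a hospital admission the participant considers unrelated would never reach the physician. The documents do not support that: an admission is plainly a notable medical event, and 8.2.1 sends notable spontaneous reports into the 8.2.2 process, where the investigator and physician judge causality. What remains is the difference between asking and waiting to be told. It matters most for events a participant would not think worth a call.

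Other points also stand:

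- SEC symptoms are recorded during treatment regardless of relatedness, so it would be wrong to say that all unrelated events go unasked.
- The form itself is not in the documents. Section 8.2.1 also says each assessment inquires about any event since the last in-person visit. Read in context, that sentence sets the look-back window. If it was meant to set the scope, it conflicts with the preceding restriction and the wording still needs correcting.
- Medication changes are reviewed at every in-person visit and may bring illnesses to light, but 8.2.1 does not list this as an AE method.
- The pre-Baseline interval is short and precedes counselling and patch use. Scan 1 itself is attended by staff.

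Two stronger readings should be resisted. Adding 18 weeks and 1 week to state the share of participation without SEC questioning would mislead: all of those weeks are off patch, when a patch checklist is least expected, and the sum assumes that 8.2.1 rather than 6.5.2 governs SEC timing. A reader might also infer bias between arms, because participants' beliefs about cause could differ by counselling condition. The statistical methods in 6.10 specify no between-arm AE comparison, both arms receive the same open-label patch, and 6.5.2 refers to protecting the blind on counselling condition.

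**Conclusion.** The point holds as a mismatch between the protocol's AE definition, its capture statement and its scheduled questions. It has three parts:

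1. Events not on the SEC that the participant thinks unrelated are not actively asked about at any visit.
2. SEC-type symptoms are not asked about at weeks 12 and 26 if 8.2.1 and 6.2.12 govern. Section 6.5.2 says otherwise, so SEC timing is unresolved rather than settled.
3. Events in the week or so between Intake and Baseline, including after Scan 1, lie outside both look-backs.

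For these, capture rests on participants volunteering notable events. That reduces the gap without justifying a claim to capture all AEs and SAEs. The number of events missed cannot be estimated from the documents. The conclusion assumes that the form follows the scope described in 6.5.2 and 8.2.1. The change should be made because it corrects a stated rule that contradicts the protocol's own definition.

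**What to change.** - In 6.5.2 and 8.2.1, reword the open question to ask about any new or worsened symptom, illness, injury, or hospital or emergency visit, whether or not the participant thinks it is related. Leave relatedness to the investigator and physician, as 8.2.2 already does.
- Reconcile when the SEC is given across 6.2.12, 6.5.2 and 8.2.1. At any visit where it is not given, remove the open form's exclusion of SEC items.
- Run the look-back of the first AE form from the first study procedure, so that it covers Intake to Baseline and Scan 1.

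The cost is form and protocol wording, with no added visit or procedure. The downside is more minor, unrelated events to document and follow up.

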8.2.2 AE/SAE Documentation and Internal Reporting Procedures

AE/SAE Documentation: As noted above in section 8.2.1, research staff are trained to collect follow-up information about any **severe, moderate, or select mild side effects** reported on the SEC Form, **any medical event(s) reported on the Open-Ended AE Form, or any notable spontaneously reported medical event or concern.** At a minimum, follow-up information will include AE/SAE onset/resolution, description of event/course, severity, action taken, outcome, and possible relation to TN treatment (if applicable).

Information surrounding AEs and SAEs will be initially recorded on the appropriate source document such as the SEC Form, Open-Ended AE Form, an "AE Note" or SAE Form, and/or any document in which the AE/SAE information was originally recorded. All applicable AEs and SAEs will then be documented on a cumulative AE and SAE log maintained within the regulatory binder.

Completed documentation of applicable AEs will include the following information:

- Protocol Title and IRB#
- Subject Identifier
- Event Title
- Date Site Notified
- Event Start Date and Time
- Event Stop Date and Time
- Description of Event/Course (including sequelae)
- Severity:
 - None = No concerns
 - Mild = Side effect or issue does not interfere with usual daily activities

CONFIDENTIAL

This material is the property of the University of Pennsylvania. Do not disclose or use except as authorized in writing by the study sponsor

- Moderate = Side effect or issue interferes with some activities
- Severe = No normal activities are possible
- Relatedness to the study procedures (PI and/or Study Physician):
 - Unrelated = Definitely not related
 - Unlikely = Doubtfully related
 - Possibly = May be related
 - Probably = Likely related
 - Definitely = Related
- Expectedness per protocol and/or consent
 - Expected/Anticipated
 - Unexpected/Unanticipated
- Action(s) taken (if appropriate)
- Outcome (if appropriate)

Documentation of SAEs will include the following information on a standardized SAE Form:

- Protocol name and number
- Subject identifiers
- Demographic data
- TN Lot number, expiration date, and other descriptive information (if appropriate)
- Date Site Notified
- Date and time of SAE onset
- Date and time of SAE resolution, if available
- Course/Description of Event (including sequelae)
- Action Taken
- Outcome
- Follow-up plan
- Serious Status (What makes the event an SAE)
- Severity of the event
 - None = No concerns
 - Mild = Side effect or issue does not interfere with usual daily activities
 - Moderate = Side effect or issue interferes with some activities
 - Severe = No normal activities are possible
- Relatedness to the study procedures (PI and/or Study Physician):
 - Unrelated = Definitely not related
 - Unlikely = Doubtfully related
 - Possibly = May be related
 - Probably = Likely related
 - Definitely = Related
- Clinical assessment of subject conducted at time of SAE (if appropriate)
- Results of any laboratory tests and/or diagnostic procedures (if appropriate)
- Autopsy findings (if appropriate)
- Concomitant medications and therapies (excluding treatment of event)
- Relevant Medical History (if appropriate)

Internal Reporting Procedures: All relevant follow-up information outlined above (see AE/SAE documentation) concerning applicable AEs, including all information regarding the occurrence of concurrent smoking and TN (if applicable) and previously reported event(s) and/or side effects, will be reported to the Study Coordinator (or other senior personnel), Principal Investigator, and

CONFIDENTIAL

This material is the property of the University of Pennsylvania. Do not disclose or use except as authorized in writing by the study sponsor

Study Physician to determine a course of action (e.g. continue to monitor, reduce medication dose, stop medication), relatedness (causality) to the study, and expectedness (if not already established). This consult will be documented via email. The clinical course of each event will be followed until resolution, stabilization, or until it has been determined that the study treatment or participation is not (or unlikely) to be the cause.

SAEs that are still ongoing at the end of the study period must be followed up to determine the final outcome unless it has been determined that the study treatment or participation is not the cause. Any SAE that occurs after the study period and is considered to be possibly related to the study treatment or study participation should be recorded and reported immediately per this protocol.

